**REVISION HISTORY**

*This Revision History table is provided for the benefit of study team version control. If this table will not be useful please delete it.*

Revision #	Version Date	Summary of Changes	Consent Change?

## STUDY INFORMATION

### 1.0 Study Summary\*

### 2.0 Objectives\*

#### 2.1 Purpose, specific aims or objectives: *Describe the purpose, specific aims, or objectives. If more than one objective be sure to list separately.*

This is a post-market study to provide breast pumps to residents at a pediatric academic medical center as an additional layer of support in reaching lactation goals. Residents that do not have flexible break times and/or reliable close and secure pumping space face barriers to reaching their lactation goals. Wearable pumps provide users autonomy and flexibility regarding their pumping schedules. These devices are not covered as a "free" breast pump through most insurance companies and, while discounted, are often still at a higher price point for most new parents. By providing these for free to users, we expect to see the institutions' metrics regarding duration of pumping and satisfaction with meeting goals will be higher than national metrics. In partnership with Willow, our institution will provide free pumps to individuals as part of a study including participant consent.

Among medical residents and fellows during the study window of 3 years (one year providing devices and up to three years collecting data, tracking users through end of pumping experience), who have delivered a baby. Does access to a wearable Willow pump improve lactation experience and meeting goals regarding duration of pumping/providing milk?

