#### 3.2 *Describe any relevant preliminary data.*

Relevant preliminary data is outlined in the following literature study and experience from other institutions using a current model of a recycling program has successfully supported 70 individuals at this institution. This model will be shared with other institutions as well to create mirror projects and expand the data by providing new pumps to users. National data does not look at wearables or the impact of pumping at work specifically only breastfeeding in general, this study would fill a gap in that knowledge regarding supporting work.

**3.3** *Provide the scientific or scholarly background for, rationale for, and significance of the research based on the existing literature and how it will add to existing knowledge.*

The AAP, HP2030 and WHO lactation recommendations of six months exclusive breastfeeding up to two years of breastfeeding with table food, are based on decades of research regarding health outcomes for both the lactating parent and infant. Research shows that for the infant, the short-term benefits of lactation (described as 3 to 6 months of exclusively consuming human milk) include building important immunities against common illness in the first year of life and reducing the risk of ear infections, gastroenteritis, Respiratory Syncytial Virus (RSV), Crohn's disease, eczema, diarrhea and childhood cancers. Short-term benefits for the lactating parent include quicker recovery from giving birth, increased bonding with the infant, and lower risk of postpartum depression. Long-term lactation, described as exclusively consuming human milk for six to 24+ months, provides lifetime health benefits for the infant including lower risk of asthma, diabetes, Sudden Infant Death Syndrome (SIDS), as well as, providing important nutrition (protein, calcium, vitamin a) and enhancing brain development.

This evidence has also shown that infants who exclusively consume human milk for six months had higher IQs (intelligence quotient) compared to those who consumed human milk for less than six months. Lactation can also provide emotional support for infants as a soothing tool and physical comfort during teething. Long-term health benefits for the lactating parent

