include decreased risk for cancers (breast, ovary, endometrial, thyroid), type 2 diabetes, osteoporosis, cardiovascular disease, high blood pressure, and high cholesterol. Successful long-term lactation for working parents includes pumping 2-3x per day to maintain milk production and creating a supply for the infant to consume when away from the providing parent.

Even with this research and education during pre- and post-natal visits with the healthcare team, it can be difficult to balance lactation, returning to work, and creating a pumping schedule. A recent study showed that Hispanic (48.4%), Black (35%), Native American (37.3%), White (52.3%) or Asian (71%) mothers stop lactation by six months. With more women in the workplace than ever before, returning to work after a birth is extremely common and employers must work to create welcoming environments for new parents.

Healthy People 2030 has set the goal that 42.4% of infants in the United States are provided human milk exclusively for the first six months, but as of 2020 only 25.4% of infants have reached this milestone. The Center for Disease Control and Prevention (CDC) data reported from the National Immunization Survey reports that nationally 58.2% of infants receive “any milk” through 6 months of life and in Kansas, this rate is 61.6%. While many parents set a goal of six months, there is a wide range of individual goals that new mothers may set based on circumstances. One of the questions asked in this study is intent vs. actual pumping goal since this is another area that has not been explored. According to the CDC, 60% of mothers do not reach their lactation goal. In a 2012 study conducted by the San Diego Breastfeeding Center, researchers discovered that 85% of the parents in their cohort intended to pump for 3 or more months but only 32.4% met their intended goal. These data reinforce the fact that providing human milk exclusively while returning to work is a monumental task that requires resources, commitment, and support.

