#### Inclusion Criteria

Participant eligibility will be based on employment or enrollment in a CMKC residency or fellowship program. Participant eligibility will be obtained via self-enrollment, individuals will self-identify and notify investigators when they are going to start pumping. Some parents are proactive and plan out ahead of time their lactation needs, some pivot from original plan after returning to work and request support after initiation, intervention will accommodate both and surveys will begin at pumping initiation.

The specific population of study will be individuals of birthing age that give birth while in a CMKC residency or fellowship program and have determined that they plan to provide human milk and pump at work post-delivery.

**7.2 Equitable Selection:** *Inclusion/exclusion criteria should be both fair and appropriate to the research question. If the study involves inclusion/exclusion criteria based on demographic characteristics such as sex, race/ethnicity, language, provide rationale for the criteria. For example, if excluding non-English speaking participants, provide rationale for why it is not possible to include non-English speaking participants.*

**7.3 Vulnerable Populations:** *Check any vulnerable populations that are being targeted for enrollment into the study: (Members of the following populations may not be included as participants in the research unless selected here.)*

 Children/Minors (under 7 years of age)	 Non-Viable Neonates (infants less than 30 days old)
 Children/Minors (7-17 years of age)	 Wards of the State
 Neonates (infants less than 30 days old)	 Fetuses
 Neonates of Uncertain Viability (infants less than 30 days old)	 Pregnant Women

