We will provide a Ceres Chill with each willow pump to allow moms the ability to keep milk cold throughout the work day without needing a fridge. The item will be distributed at the beginning of the study with the willow pump. The maximum value of the item is \$70.00. Willow INC is providing a Willow GO wearable Pump. The maximum value of this item is \$349.99.

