## 28.0 Statistical Analysis\*

**28.1** *Describe the data analysis plan, including any statistical procedures or power analysis.*

We plan to examine changes in professional fulfillment and burnout using repeated measures t-test. We also plan to utilize descriptives and qualitative comments to show evidence of whether the Willow device helps the participant reach their lactation goals.

**28.2** *Describe how the sample size for the study was determined (e.g. formal sample size calculation, convenience sampling). To minimize the risks associated with a possible breach of confidentiality, appropriate sample size calculations limit the amount of patient data being recorded to the amount necessary to answer the research question.*

For all the planned analyses, having a study sample of 125-150 will be sufficient. This presents the goal for each site to have 20-25 participants over the next two years.

•
---

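### A difference from national figures cannot be credited to the Willow pump: one self-selected group, bundled support, and national data that do not cover pumping at work

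*Protocol*

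**What the plan says.** Protocol section 2.1 states the expectation that the institution's "metrics regarding duration of pumping and satisfaction with meeting goals will be higher than national metrics". It then puts the research question causally: "Does access to a wearable Willow pump improve lactation experience and meeting goals regarding duration of pumping/providing milk". Section 28.1 plans "descriptives and qualitative comments to show evidence of whether the Willow device helps the participant reach their lactation goals".

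On the comparison data, section 3.2 says: "National data does not look at wearables or the impact of pumping at work specifically only breastfeeding in general". Section 3.3 gives two national figures. One is per infant ("nationally 58.2% of infants receive" any human milk through six months). The other is per mother (60% do not reach their lactation goal).

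On who takes part, section 7.1 limits entry to residents and fellows who "have determined that they plan to provide human milk and pump at work post-delivery". It relies on self-enrolment and accepts women who ask for support after they have returned to work. The enrolment table in section 8.1 has one group, and its second column is empty.

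On what participants receive besides the pump, section 18.3 says "We will provide a Ceres Chill with each willow pump". Section 6.0 adds educational materials and access to manufacturer experts.

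**The concern.** The research question asks for the effect of a device, but the design contains nothing that shows what the same women would have achieved without it. The only external yardstick named in the aims is national data, which differ from the study in three ways: who is counted, what is measured, and what support is given. If the report places the study's rates beside national ones and answers the section 2.1 question from the gap, it credits the pump with whatever is due to prior intent, profession, late entry or the other parts of the package.

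This matters because section 5.1 foresees national presentation and journal publication, and sharing of results with the manufacturer that supplies the pump. A statement that the device helps would be read as a finding.

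**Working it through.** **1. What differs between study and reference**

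| | National figures (3.3) | Study |
|---|---|---|
| Unit, six-month feeding | infants: 58.2% | trainees who intend to pump at work |
| Unit, goal attainment | mothers in general: 100% - 60% = 40% reach goal | self-enrolled trainees |
| Subject matter | breastfeeding in general (3.2) | pumping at work |
| Entry | none described | surveys begin when pumping begins; joining after return to work allowed (7.1) |
| Support | none described | pump, chiller, education, experts (6.0, 18.3) |

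No row isolates the pump.

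**2. Illustration: six-month feeding**

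The protocol does not say what share of infants nationally ever start human milk. Call it *s* and assume 75-95%. The rate among starters with no pump effect is then 58.2% / *s*. The last two columns give the exact binomial chance that a study of a pump with no effect ends above 58.2%. That means at least 15 of 25 (25 × 0.582 = 14.55) or at least 73 of 125 (125 × 0.582 = 72.75). The sizes come from section 28.2: 20-25 per site and 125-150 overall.

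| Assumed *s* | 58.2% / *s* | Gap (points) | n = 25 | n = 125 |
|---|---|---|---|---|
| same population | 58.2% | 0 | 51% | 52% |
| 95% | 61.3% | 3.1 | 64% | 78% |
| 90% | 64.7% | 6.5 | 76% | 94% |
| 85% | 68.5% | 10.3 | 87% | 99% |
| 80% | 72.8% | 14.6 | 95% | >99% |
| 75% | 77.6% | 19.4 | 99% | >99% |

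**3. The opposing force**

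Sections 3.3 and its subsection on residents describe short leave (6-8 weeks under most boards), no protected pumping time, and weeks averaging 60 and reaching 80 hours. Suppose these barriers cut continuation by a relative amount *r*. The no-effect rate becomes (58.2% / *s*) × (1 - *r*), which equals 58.2% when *r* = 1 - *s*. A relative reduction of 5-25% would therefore cancel the starter effect over the assumed range. With *s* = 90% and *r* = 15%, the rate is 64.7% × 0.85 = 55.0%, below the national figure. A pump that works could then look useless. The protocol gives neither *s* nor *r*.

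**4. Illustration: goal attainment**

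This figure is per mother, so the starter correction does not apply. The reference is 40%, and exceeding it takes at least 11 of 25 or 51 of 125.

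| Assumed rate without any pump effect | n = 25 | n = 125 |
|---|---|---|
| 50% (more committed than average) | 79% | 98% |
| 40% (same as national) | 41% | 46% |
| 32.4% (rate in the 2012 cohort cited in 3.3, used only as a low value) | 15% | 3% |

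With no device effect at all, the observed rate may almost always exceed the national one or almost never do so, depending on an unknown baseline.

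**The case against.** The strongest reply is that the protocol never makes national figures a test. Section 2.1 states an expectation. The hypotheses in 2.2 do not mention national data, and 28.1 sets no threshold and already plans descriptive analysis for goals. This stands. A reader might infer that the study succeeds if it beats the national rate, with an inflated type I error. The documents contain no such decision rule.

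Nor are national figures the only reference. Section 3.3 announces a comparison of intended with actual pumping, section 5.2 collects goals at intake, and the outtake survey covers expectation against reality. That also stands. But reaching one's own goal still does not show what would have happened without the pump.

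Three further inferences are tempting and unsupported:

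- That the comparison necessarily favours the pump. Selection on intent and late entry probably do so, but the trainee barriers the protocol describes pull the other way.
- That a built-in gap of a known number of points exists. Every gap in the first illustration rests on an assumed starting share, and 2.1 does not name 58.2% as its benchmark.
- That the earlier residency program, where 31/41 users intended seven months or more, proves a population above the national average. The protocol gives no national figure for intention.

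The protocol also partly acknowledges bundling: 2.1 presents the pump as one added layer of support, and the 2025 literature update in 3.3 stresses rooms and information. Yet the question in 2.1 and the wording in 28.1 name the device alone. Exact intervals could be left to an analysis plan. The aim and its comparator are protocol content and are stated here.

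**Conclusion.** The point holds as one of aim and interpretation. A difference from national figures, in either direction, cannot be attributed to the Willow pump. The group is self-selected on the behaviour being measured, the support is bundled, there is no comparison group, and by the protocol's own account the national data do not address pumping at work.

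This conclusion needs no assumed number; it follows from sections 2.1, 3.2, 6.0, 7.1, 8.1, 18.3 and 28.1 read together. The illustrated shift of about 3 to 19 points depends entirely on an assumed 75-95% starting share and ignores trainee barriers. It shows that the distortion could be large, not how large it is. Upward bias is likely but not proven.

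**What to change.** Reword 2.1 and 28.1, and the matching causal hypothesis in 2.2:

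- **Aim.** Replace the expectation of exceeding national figures, and the language of improving and helping, with a descriptive aim: to estimate, with exact 95% confidence intervals, the share of program users who meet the goal they set at intake, and the shares still pumping at 6 and 12 months.
- **Attribution.** Report results as those of the program (pump, chiller, education and expert support), not of the device.
- **National figures.** Show them as context only, stating that one is per infant, the other per mother in general, and neither specific to pumping at work.
- **Other references.** The earlier residency program in 3.3 (23/41 = 56% pumping beyond seven months; 75% meeting or exceeding goal) may be shown as a similar program. It also supplied wearable pumps, so it is not a no-pump control. The 221 physicians in the cited survey who used only a traditional pump are a closer reference, but the protocol gives no success rate for them.

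The cost is wording only, with no added participants or data collection. The downside is that the study can then make no causal or superiority claim for the device.

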#### 2.2 Hypothesis: *State the hypotheses to be tested.*

Using a wearable breast pump will allow working mothers to continue in their professional obligations and reach their pumping goal.

Secondary: Working mothers' burnout will not increase during the use of wearable breast pump.

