## 25.0 Withdrawal of Participants\*inclusio

**25.1** *Describe anticipated circumstances, under which participants will be withdrawn from the research without their consent.*

*A subject can withdraw at any time during the study without being required to return the device.*

**25.2** *Describe procedures that will be followed when participants are withdrawn from the research, including data retention plans or partial withdrawal from procedures with continued data collection.*

*If the subject leaves to the institution (institutional email is deactivated) they will be terminated from the study unless they notify the institution of the transition to remain in the study and provide a new email.*

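### The hypothesis that burnout does not rise is paired with a test of zero change, and no rule says what result would support it

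*Protocol*

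**What the plan says.** Section 2.2, which asks for the hypotheses to be tested, gives as the secondary one: "burnout will not increase during the use of wearable breast pump".

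Section 28.1 names one inferential method: "We plan to examine changes in professional fulfillment and burnout using repeated measures t-test". The descriptive statistics and qualitative comments in the same section are assigned to lactation goals, not to burnout.

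Section 28.2 says of size: "For all the planned analyses, having a study sample of 125-150 will be sufficient", and then: "This presents the goal for each site to have 20-25 participants over the next two years". No alpha, power, effect size, SD or margin accompanies these figures.

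The Table of Events (section 5.2) marks well-being at the monthly and outtake surveys and not at intake. The survey descriptions in sections 6.0 and 10.0 name no burnout instrument and list no burnout items at intake.

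**The concern.** The hypothesis asserts that something does not happen. The usual null of a paired t-test is that mean change equals zero. Failing to reject that null means only that the data do not rule out zero; the same data may also be compatible with a rise that matters. Smaller or noisier samples make a non-significant result more likely, so imprecision would favour the hoped-for answer.

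At stake is whether the study can say anything reliable about burnout. With no margin and no stated criterion, nothing in the protocol separates a result that supports non-increase from one that is merely inconclusive.

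**Working it through.** **The plan's own figure.** The 125–150 cannot be reproduced, because section 28 gives none of the inputs that a calculation needs.

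**Inputs**
- Pairs: 125–150 in total and 20–25 per site (section 28.2).
- Level: two-sided 0.05, assumed. One-sided 0.05 is shown as a variant.
- True rise: 0.1 to 0.5 SD of the change score, assumed.
- Loss: none in the main figures. No rate is stated, but section 25.2 names one cause: "If the subject leaves to the institution (institutional email is deactivated) they will be terminated from the study", unless they give notice and a new address. As scenarios, 100 and 88 pairs are 80% and about 70% of 125.

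**Step 1: chance that a true rise is not significant.** For n pairs and a rise of d SD, the test statistic follows a noncentral t with n − 1 degrees of freedom and noncentrality d√n. Power is the probability that it exceeds the 97.5% point of the central t; the chance of a miss is 1 − power.

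- n = 125, d = 0.2: noncentrality 0.2 × √125 = 2.236, power 0.602, miss 0.398.
- n = 150, d = 0.2: noncentrality 0.2 × √150 = 2.449, power 0.682, miss 0.318.
- n = 125 and 150, d = 0.3: power 0.914 and 0.955, miss 0.086 and 0.045.

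| Pairs | 0.1 SD | 0.2 SD | 0.3 SD | 0.5 SD |
|---|---|---|---|---|
| 20 | 94% | 87% | 75% | 44% |
| 25 | 93% | 84% | 70% | 33% |
| 88 | 85% | 54% | 21% | <1% |
| 100 | 83% | 49% | 16% | <1% |
| 125 | 80% | 40% | 9% | <1% |
| 150 | 77% | 32% | 5% | <1% |

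With one-sided 0.05, the miss rate for 0.2 SD at 125–150 falls to 21–28%. The rise detectable with 80% power (two-sided) is 0.23–0.25 SD at 125–150 and 0.58–0.66 SD at 20–25.

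**Step 2: what the same data could show against a margin.** Conclude non-increase if the upper limit of the two-sided 95% interval for mean change is below a margin of m SD. The half-width is t(0.975, n − 1)/√n, which is 0.177 SD at 125 and 0.161 SD at 150. With true change zero, power is the noncentral-t probability with noncentrality m√n.

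| Assumed margin | Power at 125 | Power at 150 | Pairs for 80% power |
|---|---|---|---|
| 0.2 SD | 0.602 | 0.682 | 199 |
| 0.25 SD | 0.792 | 0.860 | 128 |
| 0.3 SD | 0.914 | 0.955 | 90 |

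Normal-approximation check for 0.2 SD: ((1.960 + 0.842)/0.2)² = 196.3, so 197, close to the exact 199.

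Whether 125–150 is enough for this hypothesis therefore depends on a margin that the protocol does not state.

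**The case against.** The best defence is that section 28.1 only says changes will be examined. It never says that p > 0.05 will count as support. A paired t-test also yields the mean change and its confidence interval, which is what a margin-based rule needs, and margins and reading rules are often set in a statistical analysis plan, which may exist. The hypothesis is secondary, and the study is rated as not greater than minimal risk (section 17.1).

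Much of this stands, and it rules out three stronger readings.

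- A reader might infer that the plan, as written, would declare non-increase from a non-significant test. That is an inference; no decision rule is written.
- A reader might infer that a real rise would often be missed at the planned size. At 125–150, the only size tied to all the planned analyses, this holds for rises of about 0.2 SD or less, not for 0.3 SD or more. A single-site analysis of 20–25 is not described. Nor is one of 60–75, which is 3 × 20–25 if only this site and the two other schools in section 5.1 took part. Miss rates at those sizes are conditional on assumptions.
- A reader might infer that the paired design cannot support the hypothesis. It can, if burnout clearly falls or if the upper confidence limit lies below a justified margin.

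The mismatch itself survives. The protocol states both the hypothesis and the test, so this is not simply detail deferred to another document.

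**Conclusion.** The point holds in this limited form: a hypothesis of no increase is matched to a test with a zero-change null, and the protocol offers no criterion by which a result would support it. This logical gap does not depend on sample size. Its practical size does: at the stated total it matters for small rises, and it grows if pairs are lost or sites are analysed separately. The percentages rest on an assumed two-sided 0.05 level and on rises expressed in SDs of change, since the protocol gives neither a level nor an SD.

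It should be fixed, but it does not threaten the study as a whole. The lactation-goal question is to be answered descriptively and is unaffected.

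**What to change.** Keep the paired analysis and add to section 28.1 wording such as:

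> Non-increase of burnout will be concluded only if the upper limit of the two-sided 95% confidence interval for mean change from [named baseline survey] is below [margin, in points of the named burnout scale]. Otherwise the estimate and interval will be reported without a claim of no increase. A p-value above 0.05 will not be taken as support.

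Three things go with it.

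1. **Margin.** Name the burnout scale and set and justify the margin before any data review. Sections 24.3 and 31.2 plan quarterly looks, and a margin chosen after them would not be credible.
2. **Baseline.** Reconcile the change score with the Table of Events: either add the burnout items to the intake survey, or define the first monthly survey as baseline. The survey attachments are not available here; if they already carry burnout items at intake, only the table needs correcting.
3. **Sample size.** Replace the general statement about "having a study sample of 125-150 will be sufficient" with a check against the chosen margin, allowing for lost pairs.

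The cost is a few sentences, one margin and possibly a few baseline items in an existing survey. The claim also becomes harder to make: under a tight margin the study may have to report an inconclusive result.
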